4.4.1 Administrative, Behavioral, and Regulatory Procedures

- Ongoing informed consent:
 - -As needed at all visits
- Locator information:
 - -At all visits and contacts.
- Behavioral risk assessment:
 - -Quarterly.
- HIV/STD counseling, condoms, other prevention supplies:
 - -Quarterly.
 - -Additionally when needed/requested.

4.4.2 Clinical Procedures

- Interval (i.e., since last visit) medical and menstrual history and concomitant medication review:
 - -At all visits.
- Pelvic exam with:
 - colposcopy (at selected sites);
 - specimen collection for Gram stain;
 - wet mount for BV, candidiasis, and trichomoniasis; and
 - swab for multiplex PCR if genital ulcer is observed:
 - -Quarterly.
 - -Additionally when clinically indicated.

- Urine collection:
 - -At all visits.
- Blood collection:
 - -Quarterly.
 - -Additionally when clinically indicated.
- Test results disclosure:
 - -As needed at all visits and contacts.
- Treatment for STDs and other infections (except asymptomatic candidiasis); offer of STD testing and treatment for partner(s):
 -When clinically indicated.

4.4.3 Laboratory Procedures

- Urine pregnancy test:
 - -At all visits.
- Urine LCR for chlamydia and gonorrhea:
 - -Quarterly.
 - -Additionally when clinically indicated.
- Dipstick urinalysis; urine culture if dipstick is positive for leukocytes or nitrites:
 - -When clinically indicated.
- Gram stain assessment for BV according to the Nugent criteria at the HPTN Central Lab:
 - -Quarterly.
 - -Additionally when clinically indicated.
- Multiplex PCR at the HPTN Central Lab:
 - -When a genital ulcer is observed.
- HIV serology:
 - -Quarterly.
 - -Additionally when clinically indicated.

Note: For participants who test HIV-positive at study Month 3, HIV antibody testing will be performed on plasma archived at the participants' Enrollment Visits, to confirm that the participant was HIV-uninfected at enrollment; if additional testing (e.g., RNA PCR, p24 antigen) is required to clarify participants' HIV status at enrollment, such testing will be undertaken in consultation with the HPTN Central Lab.

- Syphilis serology:
 - -Quarterly.
 - -Additionally when clinically indicated.
- Plasma archive:
 - -When phlebotomy is performed for confirmatory HIV testing (i.e., when "sample 2" in Appendix II is obtained).
 - At study exit.

Note: For participants who do not consent to long-term specimen storage and possible future research testing, archived plasma will be discarded after all protocol-required and quality assurance testing has been completed (see also Section 8.3).

4.5 Interim Contacts and Visits

Interim visits may be performed at any time during the study. Depending on the type of visit, site capacity, and site and participant preferences, interim visits may take place at the study site or at community-based locations. Interim visits may occur:

- For administrative reasons, e.g., the participant may have questions for study staff or may need to re-schedule a follow-up visit.
- For interim STD counseling and testing in response to STD symptoms.
- For interim HIV counseling and testing in response to presumed exposure to HIV.
- To provide participants with the results of confirmatory HIV test results, per the algorithm in Appendix II.
- In the event that a participant presents to the study site after having missed a scheduled visit (e.g., in response to locator/tracing efforts) on a day that does not fall within a scheduled visit window.
- To complete pelvic exam and HIV counseling and testing procedures after a missed quarterly visit.
- For other reasons at participant request.

All interim contacts and visits will be documented in participants' study records and on applicable case report forms.

4.6 Final Contact

As indicated above, the results of laboratory tests performed at study visits will be provided to participants at their next monthly visit. Depending upon when a site transitions from this study to HPTN 035, some participants will not have received the results of tests performed at their last visit prior to the transition. In such cases, study staff will contact participants with pending test results and deliver their results and appropriate treatment in a timely manner.

5 SAFETY MONITORING AND ADVERSE EVENT REPORTING

The study site Investigators are responsible for continuous close safety monitoring of all study participants, and for alerting the protocol team if unexpected concerns arise. The protocol team will meet via conference call every two to four weeks during the period of study implementation, and additional ad hoc calls will be convened if required. Since this is an observational study in which participants will not receive any investigational agents, no adverse event reporting will be undertaken.

6 STATISTICAL CONSIDERATIONS

6.1 Review of Study Design

This is a prospective cohort study. Accrual of 240 participants at each participating study site will be completed over the course of six months. Each participant will complete a minimum of six and a maximum of 12 scheduled monthly follow-up assessments. The total length of the study will be 12-18 months.

6.2 Endpoints

6.2.1 Primary Endpoints

Consistent with the primary study objective, HIV seroconversions observed during the study follow-up period will be assessed as primary endpoints.

6.2.1 Secondary Endpoints

Consistent with the secondary study objectives, the following will be assessed as secondary endpoints:

- Potential participants screened for the study, and the screening outcome for each screenee.
- Participants enrolled in the study.

- Participants retained in the study until the site-specific study end date.
- Demographic characteristics of women screened for and/or enrolled in the study, including:
 - Age
 - Race/ethnicity
 - Educational level
 - Employment status
 - Income level
- HIV risk behaviors reported by women enrolled in the study, including:
 - Number of sex partners
 - Frequency of vaginal intercourse
 - Frequency of unprotected vaginal intercourse
 - Frequency of anal intercourse
 - Frequency of unprotected anal intercourse
- Prevalent (i.e., at screening/enrollment) and incident (i.e., during follow-up) occurrences of the following:
 - Pelvic exam findings involving deep epithelial disruption
 - Genital ulcer disease
 - Other genital signs and symptoms
 - Bacterial vaginosis
 - Candidiasis
 - Chlamydia infection
 - Gonorrhea infection
 - Syphilis infection
 - Trichomoniasis

6.3 Accrual, Follow-up, and Sample Size

Each participating study site will target accrual of 240 study participants within the six-month accrual period, with the monthly enrollment targets presented in Section 2.2. Each site also will target retention of 95 percent of enrolled participants annually (or 97.5 percent semi-annually).

As will be described in Section 6.4.2, assessment of the study outcomes related to accrual and retention will not require statistical analysis. However the precision of study estimates of HIV and STD incidence depends on the number of participants enrolled and retained in the study, as well as the "true" seroincidence rate. Shown in Tables 1 and 2 below are the widths of exact 95% confidence intervals around site-specific incidence rates, assuming the accrual schedule presented in Section 2.2 and retention of 97.5 percent of participants semi-annually, with either a sixmonth (Table 1) or twelve-month (Table 2) follow-up period, and an expected 117 and 234 woman-years of follow-up, respectively.

Table 1
95% Exact Confidence Intervals for Infection Rates
Observed in a Six-Month Follow-up Period

Observed in a dix-month i dilow-up i eriod								
No. Infections	Observed	95% Exact						
Observed	Infection Rate	Confidence Interval						
1	1.7%	0.2-6.2%						
2	3.4%	0.9-8.8%						
3	5.1%	1.8-11.2%						
4	6.8%	2.9-13.5%						
5	8.5%	4.0-15.7%						
6	10.3%	5.3-17.9%						

Table 2
95% Exact Confidence Intervals for Infection Rates
Observed in a Twelve-Month Follow-up Period

No. Infections Observed	Observed Infection Rate	95% Exact Confidence Interval
2	1.7%	0.4-4.4%
4	3.4%	1.4-6.7%
6	5.1%	2.6-9.0%
8	6.8%	3.9-11.1%
10	8.5%	5.2-13.2%
12	10.3%	6.5-15.3%

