2.2 Study Design

This is a prospective cohort study to be conducted at HPTN study sites located in Chililabombwe, Zambia; Durban, South Africa; Hlabisa, South Africa; Lusaka, Zambia; and Moshi, Tanzania. The study design and visit/procedures schedule are summarized in the Schema and in Appendix I. All procedures are consistent with those specified for implementation in HPTN 035.

Each study site will target enrollment of 240 study participants over the course of a six-month accrual period, according to the following schedule of monthly enrollment targets:

- Study month 1: 20 participants
- Study month 2: 30 participants
- Study month 3: 40 participants
- Study month 4: 50 participants
- Study month 5: 50 participants
- Study month 6: 50 participants

The study follow-up period then will extend for at least six months, and up to a maximum of 12 months, from the end of the accrual period.

It is expected that each study site will be activated to implement HPTN 035 by the end of the six-month follow-up period, however if this is not the case, the follow-up period may be extended for up to another six months, pending activation of HPTN 035. Possible reasons for a delay in activation of HPTN 035 include delays in finalizing the HPTN 035 protocol and implementation plans, delays in manufacturing and packaging the investigational products for HPTN 035, delays in obtaining ethical review and approval of the HPTN 035 protocol, and indication based on performance in this study that additional preparedness work is required prior to transitioning to HPTN 035. On a site-by-site basis, upon activation of HPTN 035, this study will be terminated and participants will be invited to screen for HPTN 035.

As described more fully in Section 3.3, potential study participants will be screened for eligibility and enrolled in the study over the course of up to 30 days, and over the course of at least one Screening Visit and one Enrollment Visit.

Enrolled participants then will complete monthly follow-up assessments throughout the duration of their participation. At each visit, participants will complete an interval medical/menstrual history and undergo pregnancy testing. HIV and sexually transmitted disease (STD) risk reduction counseling messages will be reinforced as needed and condoms and other prevention supplies will be distributed.

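### Section 6.3 says Table 1 uses the Section 2.2 accrual schedule, but its 117 woman-years counts six months per woman; the schedule gives about 168

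*Supplement*

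**What the plan says.** Section 2.2 sets the site target: "Each study site will target enrollment of 240 study participants over the course of a six-month accrual period". The monthly targets are 20, 30, 40, 50, 50 and 50, running from "Study month 1: 20 participants" to "Study month 6: 50 participants". The same section counts the follow-up period as "at least six months, and up to a maximum of 12 months, from the end of the accrual period", with each site closing when HPTN 035 is activated there.

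Section 6.1 states the limits per woman: "Each participant will complete a minimum of six and a maximum of 12 scheduled monthly follow-up assessments". It gives a total study length of 12 to 18 months. The Schema also gives 6 to 12 months per participant, and the visit schedule in Appendix I ends at month 12.

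Section 6.3 says that the interval widths in Tables 1 and 2 were obtained "assuming the accrual schedule presented in Section 2.2 and retention of 97.5 percent of participants semi-annually", for a six-month or a twelve-month follow-up period, "and an expected 117 and 234 woman-years of follow-up, respectively".

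The letter of amendment of 26 February 2003 corrects the infection counts to 2, 4, 6, 8, 10 and 12 in Table 1 and to 4, 8, 12, 16, 20 and 24 in Table 2. It leaves the rates, the intervals and the woman-years as they were. Those amended counts are used below.

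**The concern.** Under staggered entry with a common closing date, women who enter early are followed longer than women who enter late. If the base-case site closes six months after accrual ends, only a woman enrolled on the last day of accrual contributes as little as six months. A calculation that used the accrual schedule should therefore come out well above 240 half-years, yet 117 is below that.

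Estimating HIV incidence is the primary objective, and Tables 1 and 2 are the only quantitative support for 240 women per site. A reader relies on them for two things: how precise a site's rate will be if the study closes on time, and how much an extension of up to six months would add. Both answers depend on the woman-years.

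**Working it through.** **Inputs.** Monthly enrollment of 20, 30, 40, 50, 50, 50 (Section 2.2; sum 240). Follow-up to six months after the end of accrual (Section 2.2). Retention of 97.5% per six months (Section 6.3). Intervals under the Poisson distribution (Section 6.4.1), here exact. Two inputs are not in the documents and are assumed: when in the month women enroll, and how losses are spread over time.

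**Step 1: reproduce the plan's figures.**
- Table 1: 240 × 0.5 year × 0.975 = 117.0.
- Table 2: 240 × 1 year × 0.975 = 234.0.

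Both match exactly, and neither uses the accrual schedule.

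**Step 2: reproduce the printed intervals.** For x infections in T woman-years, the exact limits are χ²(0.025; 2x)/(2T) and χ²(0.975; 2x+2)/(2T). With T = 117:

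| Infections | Rate | Recomputed | Printed |
|---|---|---|---|
| 2 | 1.7% | 0.2–6.2 | 0.2–6.2 |
| 4 | 3.4% | 0.9–8.8 | 0.9–8.8 |
| 6 | 5.1% | 1.9–11.2 | 1.8–11.2 |
| 8 | 6.8% | 3.0–13.5 | 2.9–13.5 |
| 10 | 8.5% | 4.1–15.7 | 4.0–15.7 |
| 12 | 10.3% | 5.3–17.9 | 5.3–17.9 |

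The printed limits are right for 117 woman-years, apart from 0.1 in three lower limits.

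**Step 3: woman-years from the schedule.** With mid-month enrollment and closure six months after accrual ends, the six monthly cohorts have 11.5, 10.5, 9.5, 8.5, 7.5 and 6.5 months of possible follow-up.

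20×11.5 + 30×10.5 + 40×9.5 + 50×8.5 + 50×7.5 + 50×6.5 = 230 + 315 + 380 + 425 + 375 + 325 = 2050 woman-months, or 170.8 woman-years before losses.

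For exponential loss at 97.5% per half year, the hazard is λ = −ln(0.975)/0.5 = 0.0506 per year, and a woman with y years available contributes (1 − e^(−λy))/λ on average. By cohort this gives 18.7 + 25.7 + 31.0 + 34.8 + 30.8 + 26.7 = 167.7 woman-years. That is 167.7/117 = 1.43 times the stated figure.

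**Step 4: sensitivity to the two assumptions.**

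| Enrollment within month | No loss | Flat 0.975 | Exponential | Retention at end of follow-up applied to all time |
|---|---|---|---|---|
| Start | 180.8 | 176.3 | 177.3 | 173.9 |
| Middle | 170.8 | 166.6 | 167.7 | 164.6 |
| End | 160.8 | 156.8 | 158.0 | 155.3 |

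The range is 155 to 181. No variant comes near 117.

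**Step 5: precision at 168 woman-years.**

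| Infections | Rate | Exact 95% interval |
|---|---|---|
| 2 | 1.2% | 0.1–4.3 |
| 4 | 2.4% | 0.6–6.1 |
| 6 | 3.6% | 1.3–7.8 |
| 8 | 4.8% | 2.1–9.4 |
| 10 | 6.0% | 2.9–10.9 |
| 12 | 7.1% | 3.7–12.5 |

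Near 5%, the width is 9.4 − 2.1 = 7.3 points at 8 infections and 7.7 points at 9, so about 7.5. Table 1's row at 5.1% is 11.2 − 1.8 = 9.4 points wide.

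**Step 6: gain from extending follow-up.** The tables imply 234/117 = 2.0, a doubling of woman-years. With Table 1 on the schedule and each woman capped at 12 months, it is 234/167.7 = 1.40, a gain of about 40%.

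**The case against.** The best defense is that the two tables bracket the design. Section 6.1 and the Schema give each woman at least six and at most 12 months; 117 is the total if every woman has the minimum, and 234 if every woman has the maximum. The schedule-based 168 lies between them. The error is also in the safe direction, and nothing in the final analysis depends on it. The arithmetic here is accepted, and so is the direction. The defense still does not fit the text: Section 6.3 names the accrual schedule as an assumption, and no rule takes a woman out at six months while her site remains open. Table 1 can be kept as a lower bound only if it is labeled as one.

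A reader might infer more than the documents support, in four ways.

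- **That every Table 1 interval is miscalculated.** Step 2 shows otherwise. The intervals are right for the woman-years printed with them; what fails is the stated basis for those woman-years.
- **That time and seroconversions during accrual, about 30% of the total, would be left out,** because Section 2.2 starts the follow-up period when accrual ends. Section 4.4 schedules visits from each woman's own enrollment date, and Section 6.4.1 divides all confirmed seroconversions by all woman-years.
- **That Table 2 should show about 282 woman-years,** from 12 months after accrual ends with no cap per woman. The Schema, Section 6.1 and Appendix I all stop at 12 months per participant, and 234 agrees with them. Section 2.2's wording is what sits apart.
- **That retention alone disproves 117,** because averaging the loss over six months gives 240 × 0.5 × (1 + 0.975)/2 = 118.5. That is a choice of loss model worth about 1.3%, not an error.

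**Conclusion.** Section 6.3 is wrong as written. The 117 woman-years behind Table 1 does not follow from the accrual schedule it claims to assume. With follow-up to six months after accrual ends and 97.5% semi-annual retention, the expected figure is about 168 per site, 43% higher. The value 168 rests on mid-month enrollment and exponential loss, which the documents do not specify; the conclusion that 117 is too low for this schedule does not depend on either.

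The effect is confined to planning. Table 1 understates the precision of the base-case study, and the pair of tables overstates the gain from extending it. The 240 per site is not undermined, since the schedule implies narrower intervals than those printed. The incidence estimates under Section 6.4.1 are unaffected because they use observed woman-years. Table 2's 234 stands under the 12-month maximum per participant.

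**What to change.** Preferred: recompute Table 1 at about 168 woman-years, stating the assumed timing of enrollment within the month and the loss pattern, and replace the rates and intervals with those in Step 5.

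Failing that: remove the accrual-schedule assumption from Section 6.3 and label Table 1 as a lower bound that counts six months for every woman.

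In either case, reconcile Section 2.2, which allows up to 12 months from the end of accrual, with the 12-month maximum per participant in the Schema, Section 6.1 and Appendix I, and state the cap that Table 2 assumes.

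The cost is a wording change and one recomputed table in a letter of amendment. Neither option for Table 1 changes study conduct.

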6.4 Data Analysis

6.4.1 Primary Analysis

Corresponding to the primary study objective, an HIV seroincidence rate will be computed for each study site, as the total number of confirmed HIV seroconversions divided by the total number of woman-years of follow-up. Confidence intervals will be calculated based on Poisson distribution assumptions.

6.4.2 Secondary Analyses

Corresponding to the secondary study objectives, the following secondary analyses will be performed:

- The study accrual process will be described by tabulating the number and rate of potential participants screened for and enrolled in the study at each site, overall and by month during the accrual period. Each site's actual accrual rates will be compared to the target rates, and reasons for ineligibility for the study will be tabulated.
- The number of enrolled participants retained in the study will be tabulated for each site for the entire site-specific follow-up period as well as for each quarter in the follow-up period. Retention rates also will be calculated. The denominator for these calculations will be the total number of participants enrolled in the study at the site. The numerator will include all participants at the site who complete a scheduled visit during the interval and/or are known to have died during a previous interval. Retention rates for each site will be compared to the annual target of 95 percent.
- The demographic characteristics of persons screened for and/or enrolled in the study at each site will be described. At a minimum, the characteristics listed in Section 6.2 will be tabulated.
- The HIV risk behaviors of persons enrolled in the study at each site will be described. At a minimum, the frequency of each of the outcomes listed in Section 6.2 will be tabulated.
- The baseline prevalence for each of the genital signs and symptoms and infections listed in Section 6.2 will be computed for the enrolled study population at each site, as the total number of endpoints observed among enrollees divided by the number of participants enrolled. Appropriate 95% confidence intervals also will be computed. An incidence rate for each of the genital signs and symptoms and infections listed in Section 6.2 also will be computed for each study site, as the total number of endpoints observed divided by the total number of person-years of follow-up. Confidence intervals will be calculated based on Poisson distribution assumptions.

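### Section 6.4.2 divides each quarter's retention by all enrolled women, so in late quarters women with no visit due are counted as not retained

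*Supplement*

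**What the plan says.** Section 6.4.2 tabulates retention for each site "for the entire site-specific follow-up period as well as for each quarter in the follow-up period". One denominator serves both: "The denominator for these calculations will be the total number of participants enrolled in the study at the site". The numerator is "all participants at the site who complete a scheduled visit during the interval and/or are known to have died during a previous interval". The benchmark follows: "Retention rates for each site will be compared to the annual target of 95 percent". Section 6.3 gives the same target with its half-year equivalent: "Each site also will target retention of 95 percent of enrolled participants annually (or 97.5 percent semi-annually").

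The design supplies the other half. Section 2.2: "Each study site will target enrollment of 240 study participants over the course of a six-month accrual period", with monthly targets of 20, 30, 40, 50, 50 and 50. A site stays open 6 to 12 months after accrual ends and closes when HPTN 035 is activated there, which is expected by month six of that period. Section 6.1: "Each participant will complete a minimum of six and a maximum of 12 scheduled monthly follow-up assessments". The secondary endpoint list in Section 6.2 names the outcome as "Participants retained in the study until the site-specific study end date".

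Neither the 2003 letter of amendment nor the 2004 clarification memorandum changes any of this.

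**The concern.** With staggered entry and a common closing date, women reach closure after different lengths of follow-up. A woman who entered in the last accrual month may have no visit due in months 10-12. She cannot enter the numerator for that quarter, but she stays in the denominator, so the rate treats her like a woman who was lost. The authors saw that some women cannot attend a later visit, since they credit earlier deaths. They made no matching allowance for site closure or for reaching 12 months.

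Estimating retention is a stated secondary objective. Section 3.5 has the Protocol Team and the Study Monitoring Committee act on below-target retention, and Section 2.2 lists performance in this study among the reasons for delaying a site's move to HPTN 035. A late-quarter rate that mixes closure with loss would mislead that judgment.

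**Working it through.** **The plan's own figures.** Section 6.3 expects 117 and 234 woman-years per site. Both reproduce as women × years × semi-annual retention: 240 × 0.5 × 0.975 = 117 and 240 × 1.0 × 0.975 = 234. They treat every woman as followed for exactly 6 or exactly 12 months. The documents state no expected quarterly retention, so the rest applies the Section 6.4.2 rule to the Section 2.2 schedule.

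**Inputs.** Cumulative enrollment by the end of study months 1 to 6 is 20, 50, 90, 140, 190 and 240. No woman is lost. Timing of entry within a month is not given, so it is varied. Section 4.4 lets a visit be completed up to two weeks early (14/30.4 = 0.46 month).

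**Participant-time quarters, closure six months after accrual (study month 12).** A visit at participant month m falls due by closure only if entry is no later than study month 12 − m. For m = 6 that is month 6, so all 240 women are due in quarters 1 and 2, and perfect retention reads 100%. For later quarters:

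| Interval and visit counted | Latest entry | Even or end-of-month entry, no window | Even entry, visit up to two weeks early | All enter at start of month |
|---|---|---|---|---|
| Months 7-9, any monthly visit | 5 | 190/240 = 79% | (190 + 0.46 × 50)/240 = 213/240 = 89% | 240/240 = 100% |
| Months 7-9, month-9 visit only | 3 | 90/240 = 37.5% | (90 + 0.46 × 50)/240 = 113/240 = 47% | 140/240 = 58% |
| Months 10-12, any monthly visit | 2 | 50/240 = 21% | (50 + 0.46 × 40)/240 = 68/240 = 28% | 90/240 = 37.5% |
| Months 10-12, month-12 visit only | 0 | 0% | (0.46 × 20)/240 = 9/240 = 4% | 20/240 = 8% |

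**Later closure, participant time.** Closing nine months after accrual (study month 15), the limit is 15 − m. Months 7-9 read 100%. Months 10-12 read 190/240 = 79% for any visit, or 90/240 = 37.5% for the month-12 visit, with even entry and no window; with start-of-month entry these become 100% and 58%. Closing twelve months after accrual, every woman reaches month 12 and all four quarters read 100%.

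**Quarters in site time, counted from the end of accrual.** In a six-month period every woman has a visit due in both quarters, so both read 100%. In a twelve-month period the first three quarters read 100%. The last covers study months 15-18. The 90 women who entered in months 1-3 have reached 12 months by then, which leaves 150/240 = 62.5%. Late completion within the window could add only some of the 40 month-3 entrants. Even with all of them the figure is 190/240 = 79%.

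**The case against.** The best defense is that Section 2.2 describes the follow-up period as running from the end of accrual. If the quarters in Section 6.4.2 are quarters of that period, the expected six-month case is unaffected. That reading is possible, but Section 4.4 and Appendix I place quarterly visits at participant months 3, 6, 9 and 12, so the text leaves the matter open. Under site time a shortfall still remains in the last quarter of a fully extended site.

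It can also be said that 117 and 234 woman-years imply equal follow-up for all, in which case no quarter is affected. But Sections 2.2 and 6.1 describe staggered entry and 6 to 12 visits. With mid-month entry and closure six months after accrual, follow-up before loss is (20 × 11.5 + 30 × 10.5 + 40 × 9.5 + 50 × 8.5 + 50 × 7.5 + 50 × 6.5)/12 = 171 woman-years, not 120.

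A reader might infer more than the documents support:

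- That every quarter reads low. Participant quarters 1 and 2 do not, because six months of follow-up is guaranteed.
- That the whole-period rate is lowered too, with women who finish 12 months before an extended site closes counted as lost. The numerator needs a scheduled visit during the interval. Over the whole period those women have one, and the endpoint wording does not class them as lost.
- That 79% and 21% are ceilings. Start-of-month entry or early visits raise both.
- That every site would fail. The rates are compared with a target, but no pass/fail rule or activation threshold is given, and Section 3.5 provides separate weekly reports on quarterly assessments.

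Finally, this is a descriptive tabulation that can be recomputed from the visit data. That limits the harm but does not make the stated rule right.

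**Conclusion.** Wrong as written, in a secondary descriptive analysis. Under either reading of a quarter, a closing date that the design allows gives a late quarter that falls well short of 95% with nobody lost.

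- **Participant time, closure six months after accrual:** about 79-100% for months 7-9 on any monthly visit, or 38-58% if the month-9 visit is required. For months 10-12, about 21-38% on any visit, and at most about 8% for the month-12 visit.
- **Site time:** only the last quarter of a site extended to 12 months is affected, at about 62.5% ignoring the window.

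The participant-time shortfall disappears if every woman is followed to month 12. The figures assume enrollment exactly on the Section 2.2 targets. The ranges reflect timing of entry within the month and use of the visit window, neither of which the plan fixes for this purpose. The primary HIV incidence rate uses woman-years and is unaffected.

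**What to change.** In Section 6.4.2, state whether a quarter is participant time or site time, and whether any monthly visit or only the quarterly visit counts. For each quarter, use as denominator the women whose visit for that interval fell due no later than site closure and no later than their own month 12. Keep all enrolled women as the denominator for the whole-period rate.

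With closure six months after accrual, even entry and any monthly visit counting, the quarterly denominators become 240, 240, 190 and 50, and perfect retention reads 100% in each. A Kaplan-Meier retention curve censored at site closure or month 12 is an optional addition.

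The cost is one or two sentences. No new data are needed: enrollment dates fix the visit due dates, and the tracking database in Section 3.5 already supports visit scheduling and follow-up of missed visits.

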Each quarter, participants additionally will undergo a structured interview to ascertain HIV risk behaviors and receive HIV/STD pre-test, risk reduction, and post-test counseling. Participants also will undergo pelvic exams with wet mount testing for BV, candidiasis, and trichomoniasis; colposcopic evaluations will be performed at selected sites in accordance with the CONRAD/WHO Manual for the Standardization of Colposcopy for the Evaluation of Vaginal Products, Update 2000. For participants found to have a genital ulcer on pelvic exam, the ulcer will be swabbed for multiplex polymerase chain reaction (PCR) testing at the HPTN Central Lab for chancroid, herpes simplex virus 2 (HSV-2), and syphilis. Follow-up testing for chlamydia, gonorrhea, syphilis, and HIV (see Appendix II) will be performed quarterly, and additionally if clinically indicated. A sample of HIV test results will be confirmed for quality assurance purposes by the HPTN Central Laboratory.

Monthly visits other than those in which pelvic exams are scheduled may take place either on-site, in a participant's home, or at other community-based locations, depending on site capacities and site and participant preferences. If genital symptoms are reported during an off-site visit, the participant will be instructed to report to the on-site clinic as soon as possible for a pelvic exam. Other participant-initiated interim visits may occur at any time during follow-up, for example to obtain additional HIV counseling and testing.

All HIV and STD testing will be performed in the context of pre-test, risk reduction and post-test counseling. Study sites will provide this counseling in accordance with locally-accepted standards of practice and will document their counseling policies and procedures prior to study implementation for purposes of staff training, quality assurance, and study monitoring. In accordance with NIH policies, study participants must receive their HIV test results in order to remain eligible for study participation.

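### Retention over the entire follow-up period counts any one scheduled visit, so it overstates retention to the study end and contradicts the plan's own endpoint

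*Supplement*

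**What the plan says.** Section 6.4.2 tabulates retention "for each site for the entire site-specific follow-up period as well as for each quarter in the follow-up period". One denominator serves both: "The denominator for these calculations will be the total number of participants enrolled in the study at the site". One numerator serves both: "The numerator will include all participants at the site who complete a scheduled visit during the interval", together with women known to have died in a previous interval. The bullet closes: "Retention rates for each site will be compared to the annual target of 95 percent". It does not say whether the entire-period rate, the quarterly rates or both are meant.

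Three other places bear on this:

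- Section 6.2.1 (Secondary Endpoints) lists the retention endpoint as "Participants retained in the study until the site-specific study end date".
- Section 6.3 sets the target on two time scales: "Each site also will target retention of 95 percent of enrolled participants annually (or 97.5 percent semi-annually").
- Section 2.2 places HIV testing at quarterly visits and adds: "Monthly visits other than those in which pelvic exams are scheduled may take place either on-site, in a participant's home" or elsewhere in the community.

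**The concern.** The rule works tolerably for a short interval. For the entire period it asks only whether a woman was ever seen at a scheduled visit after enrolment. That is a different quantity from retention until the site's end date, and it can only be equal or higher.

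A milder form of the problem exists within a quarter. A visit in the first month of the quarter is enough, so a woman lost before the quarterly HIV-testing visit still counts as retained for that quarter.

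Estimating retention is a named secondary objective (Section 2.1.2) of a study meant to prepare sites for HPTN 035. Section 1.2 says HPTN 035 needs high retention, and Section 2.2 allows performance in this study to delay a site's transition. The figure set beside the target should therefore measure retention.

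**Working it through.** **The plan's own figures.** Section 6.3 expects 117 and 234 woman-years per site. With 240 women and 97.5% semi-annual retention, 240 × 0.5 × 0.975 = 117.0 and 240 × 1 × 0.975 = 234.0, so both are reproduced. The two targets agree: 0.975² = 95.06%.

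**Assumptions.** The documents give no loss rate. Suppose each woman has a constant monthly probability *h* of permanent loss, attends every scheduled visit until then, and is followed for the same length of time as the others. Ignore deaths. Then:

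- entire-period rate under Section 6.4.2 = P(completes Month 1) = 1 − *h*
- rate for quarter *j* under Section 6.4.2 = (1 − *h*)^(3(*j* − 1) + 1), since the first visit of the quarter is enough
- retained to month *M*, as in Section 6.2.1 = (1 − *h*)^*M*

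| Monthly loss *h* | Entire period and Q1 | Q2 | Q3 | Q4 | Retained to month 6 | Retained to month 12 |
|---|---|---|---|---|---|---|
| 0.42% (on target) | 99.6% | 98.3% | 97.1% | 95.9% | 97.5% | 95.1% |
| 1% | 99.0% | 96.1% | 93.2% | 90.4% | 94.1% | 88.6% |
| 1.27% | 98.7% | 95.0% | 91.4% | 88.0% | 92.6% | 85.7% |
| 2% | 98.0% | 92.2% | 86.8% | 81.7% | 88.6% | 78.5% |
| 4% | 96.0% | 84.9% | 75.1% | 66.5% | 78.3% | 61.3% |
| 5% | 95.0% | 81.5% | 69.8% | 59.9% | 73.5% | 54.0% |

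In a site of 240 at 5% per month, the entire-period numerator is 228. The number still present is 176 at month 6 and 130 at month 12.

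**Where the 1.27% row comes from.** It is the loss at which the second-quarter rate is exactly 95%: (1 − *h*)^4 = 0.95 gives *h* = 1 − 0.95^(1/4) = 1.27%. Retention is then 0.95^1.5 = 92.6% at month 6 and 0.95^3 = 85.7% at month 12. With six months of follow-up, Q1, Q2 and the entire period all read at least 95%, yet the site is about 5 points short of 97.5%.

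**Limiting case.** Suppose 228 women attend Month 1 only and 12 never return. The entire-period rate is 228/240 = 95.0%, and nobody is retained to the end. The quarterly rates are 95% in Q1 and 0% afterwards.

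**The case against.** The strongest reply is that the documents would not let such a site pass unseen. The same bullet requires quarterly rates over all enrolled women, and at 4% or 5% monthly loss these fall to 84.9% or 81.5% in the second quarter. Section 3.5 adds weekly reports on completion of quarterly assessments, with review by the Protocol Team and the Study Monitoring Committee. A reader might infer from the numerator that a badly leaking site would be recorded as meeting 95%. That follows only if the entire-period rate alone is held against the target, and the text does not say so. This part of the reply stands.

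It can also be said that the clause on deaths in a previous interval makes no sense for the entire period. The rule may therefore have been written for successive quarters, with Section 6.2.1 meant to govern the whole period. That is a plausible reading of the intent, but Section 6.4.2 as written applies one rule to both, so the conflict remains.

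The quarterly rates are only a partial safeguard, because they use the same any-visit rule and 95% is the only target that Section 6.4.2 names. If 97.5% were applied to the second quarter instead, the 1.27% case would be caught. A site at exactly 97.5% in Q2 would still have month-6 retention of 0.975^1.5 = 96.3%.

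On HIV testing within a quarter, Section 4.4 requires missed quarterly procedures to be made up at the next visit. That helps only women who return. Retention and completeness of testing are also distinct quantities, so this is a secondary weakness.

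**Conclusion.** The point holds as an inconsistency that makes one reported figure wrong. The entire-period rate in Section 6.4.2 does not measure the endpoint in Section 6.2.1. Under assumed monthly loss of 1% to 5%, it overstates retention by about 5 to 21 points at month 6 (99.0 − 94.1 = 4.9; 95.0 − 73.5 = 21.5) and by about 10 to 41 points at month 12 (99.0 − 88.6 = 10.4; 95.0 − 54.0 = 41.0). The quarterly rates show heavy loss but can miss moderate loss in a six-month follow-up.

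The documents do not support the stronger conclusion that the plan cannot identify a site with poor retention, for the reasons given above. Nor is the primary result computed from this numerator: Section 6.4.1 divides confirmed seroconversions by woman-years. The sizes depend on the assumed constant, permanent loss. The contradiction between the two sections does not.

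**What to change.** In Section 6.4.2:

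1. Define entire-period retention to match Section 6.2.1: women who completed their last scheduled visit due on or before the site's end date, or its make-up visit. Count those who finished Month 12 earlier as completers. Keep the existing handling of known deaths, reworded because the entire period has no previous interval.
2. For each quarter, count completion of the quarterly visit or its make-up visit, again keeping known deaths as now. Count HIV-infected women still in follow-up as retained. Section 4.4 stops their HIV serology, so a rule that required an HIV test would wrongly class them as lost.
3. Report any-visit contact separately, under that name.
4. State that the entire-period rate is compared with 97.5% at six months or 95% at twelve months.

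The cost is wording only, using data already collected. The downside is that reported retention will be lower than under the present rule.
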